6 INTERIM ANALYSES

An unblinded independent Interim Monitoring Committee (IMC) will provide oversight to ensure that the response adaptive randomization process and interim analyses perform as expected. An independent data analysis group will perform all of the interim analyses and will provide the results to the IMC.

The first interim analysis will be conducted when the first 196 subjects are randomized, again when 250 subjects are randomized, and again after each additional 50 subjects until 800 subjects are randomized. If the study reaches 800 randomized subjects, only these initial 800 subjects randomized will contribute to additional interim analyses that will be conducted every 3 months for a total of 9 months (i.e., 3 additional interim analyses). Each interim analysis will be conducted on clean data for the derived ADCOMS. The Bayesian analysis at 12 months and 18 months will be performed when all of the enrolled subjects (i.e., including any subjects who randomized after the initial 800) have been on study treatment for 12 months and 18 months, respectively, and their clinical efficacy measures evaluated.

6.1 STOPPING RULES FOR EFFICACY (EARLY SUCCESS)

The trial will be considered a success if either 1) early success is declared at an interim analysis or 2) the trial continues to completion and is declared a success at the 12 months Bayesian analysis. Since adaptive randomization decisions will be based on the 12 month treatment endpoint, a decision for early success will require that some subjects complete 12 months of treatment, and the early success decision cannot be made prior to the study randomizing 350 subjects. Interim monitoring for early success will begin at the 350 subject interim analysis. If there is greater than a 95% probability that the ED₉₀ achieves a clinically significant difference from placebo during the accrual period, the trial will stop randomization and will be declared an early success. If the trial continues to completion, the trial will be considered a success, if there is at least an 80% probability that the ED₉₀ achieves the clinically significant difference from placebo.

6.2 STOPPING RULES FOR FUTILITY

The study meets statistical futility criteria if the probability that the ED₉₀ is better than the placebo by the CSD is less than 0.05 (with ≤ 300 subjects randomized) or 0.075 (with ≥ 350 subjects randomized) at 12 months of treatment. If the study meets statistical futility criteria, the sponsor will make the final decision pertaining to study futility after reviewing recommendations

by the DSMB. Based on Sponsor's final decision, if the study continues to randomize subjects, it will be considered a failed study.

6.3 ADAPTIVE RANDOMIZATION

Subjects will receive 18 months of treatment. Randomization to placebo or one of five dose arms of BAN2401 will be fixed for the first 196 subjects randomized in the study (4:2:2:2:2:2; placebo to each of the five active arms). Randomization probabilities to each arm will be updated at each IA such that the randomization probability will be increased for the placebo arm and arms that represent the potential target dose (ED_{90}), and simultaneously decreased for other active arms. At the time of Amendment 05 of protocol, the sponsor has agreed to the request from the Voluntary Harmonisation Procedure (VHP) committee that subjects who are confirmed *APOE4* positive (*APOE4* hetero- or homozygous) not be randomized to the 10 mg/kg, biweekly dose. After each interim analysis after protocol Amendment 05, the randomization probability vector will be split between *APOE4+* and *APOE4-* strata to ensure no subjects are enrolled on the 10 mg/kg biweekly dose. The overall probabilities as suggested by RAR will still be preserved. Details on the derivation of the adaptive randomization probabilities, are found in the Simulation Plan, see [Appendix 13.2](#).

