Subjects will be from 2 clinical subgroups, collectively designated as EAD for the purposes of this protocol: (a) MCI due to AD – intermediate likelihood and (b) mild Alzheimer's disease dementia. At study entry, subjects will be stratified according to clinical subgroup, *APOE* status (*APOE4* positive and negative), and the presence or absence of ongoing AD treatment with AChEIs or memantine or both. Randomization into the 2 clinical subgroups (see [Inclusion Criteria, Section 9.3.1 of the protocol](#)) is to remain reasonably balanced whereby at least 60% of the total number of subjects will have MCI due to AD – intermediate likelihood clinical subgroup and at least 30% will have mild Alzheimer's disease dementia. The subjects will be randomized into 1 of 6 treatment groups ([Table 1](#)) as explained in [Section 9.4.4](#) and [Section 9.4.5 of the protocol](#). *APOE4* status (positive or negative) must be confirmed for all subjects prior to randomization. After Protocol Amendment 05 based on the request from the Voluntary Harmonisation Procedure (VHP) committee, subjects who are confirmed *APOE4* positive (*APOE4* hetero- or homozygous) will not be randomized to the 10 mg/kg, biweekly dose. Randomization in the Core Study will initially be fixed to each of these dose groups (4:2:2:2:2:2 ratio, placebo to each of the 5 active treatment arms). All study personnel and subjects will be blinded with respect to the dose regimens. After 196 subjects have been randomized into the study, an interim analysis (IA) will be conducted and RAR will guide subsequent randomization into dose groups. Interim analyses and RAR will be repeated after 250 subjects have been randomized and again after each additional 50 subjects until all 800 subjects are randomized, and will then be conducted at 3-month intervals until all subjects complete 12 months of

treatment. A Bayesian analysis will be conducted at 12 months of treatment to assess for early success, and at 18 months of treatment, regardless of whether early success is achieved at 12 months.

Table 1 BAN2401 Dose Regimens

Study Arm	BAN2401 Dose (mg/kg)	Infusion frequency
1	Placebo	Biweekly ^a
2	2.5	Biweekly ^a
3	5.0	Biweekly ^a
4	10.0 ^b	Biweekly ^a
5	5.0	4-week intervals ^c
6	10.0	4-week intervals ^c

a: Biweekly = 2-week intervals

b: Subjects who are confirmed *APOE4* positive (*APOE4* hetero-or homozygous) will not be randomized to the 10 mg/kg, biweekly dose.

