4.0 ALLOCATION

There will be an initial burn-in period in which patients will be allocated in blocks of 14 with 4:2:2:2:2 blocked to control and each of the 5 active dose arms respectively. There will be a total of 14 blocks and so a total of 196 patients will be randomized with 56 on the control and 28 on each of the active doses.

After this initial burn-in, adaptive randomization will begin. Adaptive randomization probabilities will be updated when 196, 250, 300, 350, 400, 450, 500, 550, 600, 650, 700, and 750 patients have been enrolled. The randomization probability for each of the 5 active doses will be weighted according to the variance components,

$$V_d = \Pr(d = d_{ED90}) \sqrt{\frac{\text{Var}(\theta_d)}{n_d + 1}} \text{ for } d = 1, 2, 3, 4, 5$$

where $\Pr(d = d_{ED90})$ is the probability the dose is the ED₉₀, $\text{Var}(\theta_d)$ is the posterior variance of the treatment effect, and n_d is the current number of subjects allocated to dose d .

- The randomization probability to the control is meant to mirror the randomization probability to the most likely ED₉₀ dose. The randomization probability for the control is weighted according to

$$V_0 = \min \left\{ \sum_{d=1}^5 V_d \left(\frac{n_d}{n_d + n_0} \right), \max(V_1, V_2, V_3, V_4, V_5) \right\} \text{ for } d = 0$$

The randomization vector is then

$$q_d = \frac{V_d}{\sum_{j=0}^5 V_j} \text{ for } d = 0,1,2,3,4,5$$

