3BM	0.01	0.252	0.602	0.381
5BM	0.008	0.161	0.585	0.348
10BM	0.009	0.168	0.593	0.355

Interim analyses are conducted again after 300 and 350 patients are enrolled and results are similar. The possibility for early success stopping begins at the 350 patient interim analysis. At the interim analysis when 400 patients have been enrolled, patients are beginning to complete the 52 weeks of follow-up for the primary endpoint (Table 7.3.A). Each of the BM doses have a positive observed effect at 39 weeks, but the 3BM dose also has a strong effect at 12 weeks and a patient with a large effect at 52 weeks. The 3BM dose is the most likely ED₉₀ (Table 7.3.B). The probability it is better than control by the CSD is 61%. Neither the early futility nor early success criteria are met. Accrual continues with the 3BM dose receiving a higher probability of randomization for the next 50 patients to be enrolled.

		No Data		6 Weeks		12 Weeks		26 Weeks		39 Weeks		52 Weeks	
	N	N	Obs	N	Obs	N	Obs	N	Obs	N	Obs	N	Obs
PBO	101	14	17	0.005	34	0.005	27	-0.012	9	-0.043	0	0	
5Q	63	12	11	-0.008	24	0.004	11	-0.001	4	-0.014	1	-0.001	
10Q	55	10	8	-0.005	18	0.016	12	-0.002	6	-0.029	1	0.208	
3BM	73	17	17	0.006	27	0.027	9	0.007	2	0.036	1	0.174	
5BM	53	11	5	0.006	18	0.014	14	0.011	3	0.095	2	-0.056	
10BM	55	7	11	0.006	17	0.007	13	0.012	6	0.086	1	0.085	

	Model Est	Pr(ED₉₀)	Pr(PBO)	Pr(CSD)
PBO	-0.005	-	-	-
5Q	0.001	0.07	0.57	0.284
10Q	0.024	0.277	0.744	0.502
3BM	0.037	0.414	0.838	0.606
5BM	0.003	0.042	0.568	0.281
10BM	0.026	0.196	0.761	0.507

Results are similar at the next interim analysis when 450 patients are enrolled. At the interim analysis with 500 patients enrolled, the 10BM dose now has the largest effect and the

randomization probabilities will shift such that the 10BM dose will receive a greater weight (Tables 7.4.A and 7.4.B).

	N	No Data		6 Weeks		12 Weeks		26 Weeks		39 Weeks		52 Weeks	
		N	Obs	N	Obs	N	Obs	N	Obs	N	Obs	N	Obs
PBO	129	17	16	0	38	0.012	26	-0.005	24	-0.001	8	0.016	
5Q	66	6	4	-0.015	24	0.005	18	0	9	0.009	5	-0.015	
10Q	69	8	10	-0.004	18	0.005	17	0.044	10	0.036	6	-0.021	
3BM	111	27	16	-0.006	40	0.018	17	0.052	8	0.026	3	0.099	
5BM	55	6	0	0	15	0.026	19	0.024	10	0.04	5	0.042	
10BM	70	9	10	0.008	15	0.02	20	0.039	10	0.007	6	0.119	

	Model Est	Pr(ED ₉₀)	Pr(PBO)	Pr(CSD)
PBO	0.017	-	-	-
5Q	-0.001	0.03	0.3	0.09
10Q	0.01	0.028	0.415	0.104
3BM	0.035	0.206	0.692	0.355
5BM	0.033	0.115	0.698	0.331
10BM	0.066	0.621	0.934	0.729

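### The promise in Section 6.3 that the overall RAR probabilities survive the APOE4 split cannot always be kept, leaves non-carrier placebo unprotected, and feeds an APOE4 imbalance into a primary Bayesian model with no APOE4 term

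*SAP*

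**What the plan says.** SAP Section 3.2 states that, after Protocol Amendment 05, confirmed APOE4-positive subjects "will not be randomized to the 10 mg/kg, biweekly dose". Section 6.3 says that after each later interim analysis "the randomization probability vector will be split between *APOE4+* and *APOE4-* strata to ensure no subjects are enrolled on the 10 mg/kg biweekly dose", and then, without condition, "The overall probabilities as suggested by RAR will still be preserved". For the calculation it adds that "Details on the derivation of the adaptive randomization probabilities, are found in the Simulation Plan".

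Section 4.0 of that plan (Appendix 13.2) contains one unstratified vector. "The randomization probability for each of the 5 active doses will be weighted according to the variance components", and the weights are then normalised over the six arms. It adds that "The randomization probability to the control is meant to mirror the randomization probability to the most likely" ED90 dose. It has no APOE4 split, non-carrier share, cap or fallback. None of the scenarios and operating-characteristic tables in Sections 8.0 and 9.0 or the two closing appendices mentions the restriction.

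**The concern.** An arm closed to one stratum can keep its overall probability only by being over-allocated in the other. If the arm is favoured enough, that required probability passes 1. Before that point, it crowds the remaining arms, which may include placebo, out of the non-carrier stratum. Non-carriers are the only newly randomized subjects who can receive 10 mg/kg biweekly, so concurrent like-for-like control becomes scarcest when the arm looks best. This runs against the appendix's aim that control should track the leading dose.

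What is at stake is the posterior probability that the ED90 beats placebo by the CSD. If the arm is largely non-carriers and its placebo comparator largely carriers, a model of arm means alone attributes any carrier difference in progression to the dose.

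**Working it through.** **Plan's own figure.** Burn-in: 14 blocks × (4 + 2 + 2 + 2 + 2 + 2) = 14 × 14 = 196, with 14 × 4 = 56 on control and 14 × 2 = 28 per active arm. This matches "a total of 196 patients will be randomized with 56 on the control and 28 on each of the active doses". The SAP gives no figure for the APOE4 split.

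**Formulae.** The first two lines are Appendix 13.2, Section 4.0. The rest follow from setting P(10 mg/kg biweekly | carrier) = 0.
- V_d = Pr(ED90) × √(Var/(n_d + 1)); V_0 = min{Σ V_d n_d/(n_d + n_0), max V_d}
- q_d = V_d/ΣV
- Preservation requires P(10 mg/kg biweekly | non-carrier) = q10/s ≤ 1
- Under any split, P(placebo | non-carrier) ≤ 1 − q10/s
- Placebo can keep q0 in non-carriers only if s ≥ q10/(1 − q0)

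**q10 and q0 at 500 patients (Tables 7.4.A and 7.4.B).** Inputs: n = 129 placebo, 66 (5Q), 69 (10Q), 111 (3BM), 55 (5BM), 70 (10BM, that is, 10 mg/kg biweekly); Pr(ED90) = 0.030, 0.028, 0.206, 0.115, 0.621 for the active arms in that order. Posterior variances are not printed; equal variances are assumed.
- V for the active arms: 0.00367, 0.00335, 0.01947, 0.01537, 0.07370
- V_0 = min(0.04193, 0.07370) = 0.04193; total 0.15747
- q10 = 0.07370/0.15747 = 0.468; q0 = 0.04193/0.15747 = 0.266

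With variance proportional to 1/n instead, q10 = 0.48 and q0 = 0.26.

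**Check without a variance assumption.** The appendix says that after this look "randomization probabilities will shift such that the 10BM dose will receive a greater weight". From 500 to 700 patients (Tables 7.4.A and 7.5.A), 10BM grows by 160 − 70 = 90 and placebo by 185 − 129 = 56. The shares are 90/200 = 0.45 and 56/200 = 0.28.

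**A milder case.** Table 9.2, One Works, means after burn-in: q10 = (153.1 − 28)/(668.5 − 196) = 125.1/472.5 = 0.265; q0 = (177.1 − 56)/472.5 = 0.256.

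**Result over an assumed range of s.** Each cell gives q10/s, then the non-carrier placebo ceiling.

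| s | q10 = 0.468 | q10 = 0.45 | q10 = 0.265 |
|---|---|---|---|
| 0.30 | 1.56, infeasible | 1.50, infeasible | 0.88, 0.12 |
| 0.40 | 1.17, infeasible | 1.13, infeasible | 0.66, 0.34 |
| 0.45 | 1.04, infeasible | 1.00, 0.00 | 0.59, 0.41 |
| 0.50 | 0.94, 0.06 | 0.90, 0.10 | 0.53, 0.47 |
| 0.60 | 0.78, 0.22 | 0.75, 0.25 | 0.44, 0.56 |
| 0.70 | 0.67, 0.33 | 0.64, 0.36 | 0.38, 0.62 |

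Placebo can hold q0 in non-carriers only from s = 0.468/0.734 = 0.64, 0.45/0.72 = 0.625 and 0.265/0.744 = 0.36 respectively.

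**Composition of the two arms.** With overall probabilities preserved, non-carriers make up at most (s − q10)/q0 of new placebo subjects. At s = 0.50 that is 0.032/0.266 = 0.12, or 0.05/0.28 = 0.18 on the realised shares. New 10 mg/kg biweekly subjects are all non-carriers. Even with placebo held at q0 in both strata, its carrier share would be 1 − s against zero in that arm.

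**Does the primary model absorb this?** Appendix 13.2, Sections 2.1 and 2.2, model the 52-week change with a mean per arm and a common variance; the longitudinal model adds only earlier visits. There is no APOE4 term, although Section 5.3.2 says that the stratification variables will be included for the primary endpoint. The same model selects the 18-month ED90 (Section 5.4.4).

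**The case against.** Three stronger readings are tempting, and the document supports none of them.

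- *The rule is impossible whenever 10 mg/kg biweekly is favoured.* It depends on s. Across the 13 scenarios of Table 9.2 the mean post-burn-in share of this arm is 0.13 to 0.265, which is feasible for any s from 0.265 up. The example trial shows what can happen at individual looks, not on average.
- *The split strips placebo from non-carriers.* Only the ceiling 1 − q10/s is forced. A loss beyond it needs a proportional split, which the SAP does not state. The other active arms can absorb the shift whenever q10/s + q0 ≤ 1. At the first look (Table 7.1; q10 about 0.14, q0 about 0.20) with s = 0.30, the sum is 0.47 + 0.20 = 0.67, so placebo need lose nothing.
- *Non-carriers are the only subjects in whom the arm can ever be compared, so dose and carrier status are inseparable.* The restriction followed a July 2014 request, and the 300-subject interim report is dated 16 June 2014, so burn-in and early RAR were unrestricted. The MMRM includes APOE4 (Sections 5.4.1.2 and 5.4.4), Section 5.3.4 plans carrier-status subgroups, and the two 10 mg regimens are combined because of the restriction.

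These points limit the concern without removing it. The MMRM does not repair the Bayesian success criterion. If the strata are imbalanced, Sections 5.4.1.2 and 5.4.4 add an MMRM without the stratification variables, and an ANCOVA on treatment and baseline is run in any case; both drop APOE4.

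Two further objections stand. The split rule may be in the protocol sections on randomization that Section 3.2 cites and that are not at hand, although Section 6.3 sends the reader to Appendix 13.2, where it is absent. And the 800-subject interim report is dated 29 September 2016, so the June 2018 SAP cannot alter the allocation.

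**Conclusion.** The concern holds in a limited form. The unconditional promise is wrong: it fails whenever q10 exceeds the non-carrier share, which in the SAP's own example means any s below about 0.45 to 0.47. Just above that, non-carrier placebo is squeezed under any split, and it can keep its intended share only from s of about 0.63 to 0.64 (0.36 for the One Works average). The cited appendix neither defines nor simulates the split, so its operating characteristics describe a different allocation rule.

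The resulting confounding of 10 mg/kg biweekly with carrier status is partial, and it reaches the primary Bayesian contrast unadjusted. Its size and direction cannot be given: the SAP states neither s nor the difference in progression between carriers and non-carriers. The feasibility results are an identity. The example's q10 of 0.47 assumes equal posterior variances, but the realised 0.45 needs no such assumption.

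**What to change.** **Wording.** Replace the sentence in Section 6.3 with, for example: *Overall RAR probabilities were preserved only where attainable given the share of APOE4-negative subjects. The split rule used at each analysis was [state it]. The operating characteristics in Appendix 13.2 do not cover this rule.* The preceding sentence should also say that it is APOE4-positive subjects who are not enrolled on the arm; as printed it excludes everyone.

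**Analysis.**
- Base the 10 mg/kg biweekly versus placebo contrast on APOE4-stratum-specific or APOE4-adjusted estimates.
- Add an APOE4 term to the 12- and 18-month Bayesian analyses, at least as a sensitivity analysis, prespecified for any result not yet unblinded. The 12-month reports listed are dated 5 December 2017, before SAP version 4.0, so a 12-month version should be labelled as added later.
- Reconcile Section 5.3.2 with the model in Appendix 13.2.

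**Reporting.** Tabulate placebo and 10 mg/kg biweekly numbers by APOE4 stratum, before and after Amendment 05.

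**Cost.** Modest extra analysis and a wider interval for that arm.

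**For a design still randomizing.** Hold placebo at q0 within each stratum and simulate the modified rule. This caps the arm's overall probability at s(1 − q0). With q0 = 0.266 the cap is 0.37 at s = 0.50, 0.29 at s = 0.40 and 0.18 at s = 0.25, against the 0.47 that RAR requests. Accrual to the arm slows, and heavily when s is small.

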7 CHANGES IN THE PLANNED ANALYSES

This document has been updated to align with updates to study protocol.

8 DEFINITIONS AND CONVENTIONS FOR DATA HANDLING

The baseline value for efficacy and safety will be defined as the most recent value reported just before first dosing.

- For subjects who start a new AD treatment (AChEIs and/or memantine) and were not on an AD treatment at randomization, a flag will be set to “Yes” at the visit where the AD treatment started and carry forward for all subsequent visits. For subjects who were on an AD treatment at the time of randomization and a dose adjustment to the AD treatment is performed after randomization, a flag will be set to “Yes” at the visit of the dose adjustment and carry forward for all subsequent visits.

The flag should be included in all efficacy data sets. The flag in the efficacy data sets will be used as a censoring mechanism for the primary endpoint described in [Section 5.4.1](#).

8.1 DEFINITION OF VISIT WINDOWS

The protocol specified visits/weeks and corresponding time windows used for visit-wise analyses are presented in terms of days relative to the first dose. For subjects that are randomized, the last available assessment on or before the date of the first dose of study drug will be used as the Baseline-Day 1.

Different assessment may have different visit schedule. A general rule for determining a time window for each scheduled visit is to split the two consecutive scheduled visits in the middle point of the two consecutive visits. For example, the time window for visit X is from the middle

point between visit (X-1) and X (exclusive) to the middle point between visit X and (X+1) (inclusive). According to protocol, “assessments should take place on the first day of the study visit in the designated study week except as noted below (footnotes h, i, and j pertaining to imaging assessments, and footnote o pertaining to CSF sample collection)” (see [page 96, Protocol Amendment 08](#)). Therefore, the scheduled day corresponding to scheduled visit at week Y is $((Y-1)*7+1)$ days. For example, the scheduled day for scheduled visit at weeks 1, 3, and 5 are Day 1, Day 15, and Day 29, respectively and the corresponding time window for scheduled visit at weeks 1 and 3 are [Day 1, Day 8] and [Day 9, Day 22], respectively

For scheduled every 3 months post baseline efficacy assessments, the analysis visits are the same as the scheduled visits. Any window rules will not apply. This is per ITT principle and also assumes that the actual assessment dates are independent from any other factors or are random and centered at scheduled time point.

For Early Termination (ET) visit and Follow Up (FU) visit, the following rules apply for efficacy assessment:

- If the last scheduled 3-month assessment before early termination (LS), ET assessment and FU assessment are in three separate sequential 3-month windows, e.g., Window(x), Window (x+1) and Window(x+2), then the analysis visits for last scheduled 3-month assessment (LS), ET assessment and FU assessment will be x, x+1 and x+2, respectively.
- If both LS and ET are in Window(x) and FU is in Window(x+1) [note: this is the most likely situation since ET and FU are expected to be separated by 3 months], then analysis visit is x for LS (per rule 1.) and (x+1) for FU and ET will not be included in Bayesian analyses and MMRM analyses.
- If LS is in Window(x) and both ET and FU are in Window(x+1), then the analysis visit is x for LS and (x+1) for one of ET and FU that is closer to scheduled (x+1) visit, another one (ET or FU) will not be included in Bayesian analyses and MMRM analyses. [Note: this scenario happens only if ET is close to window (x) and FU is within three months from ET.]

8.2 ALGORITHMS FOR EFFICACY PARAMETERS

This section describes the algorithms and missing data handling procedure to derive the totals scores for the efficacy parameters FAQ, CDR-SB, MMSE, and ADA-Cog.

FAQ: The FAQ is composed of 10 activities. Each activity is rated as 0 = Normal, 1 = Has difficulty but does by self, 2 = Requires assistance, 3 = Dependent, 8 = Not Applicable. The Total Score is the sum of the 10 activities. If any activity is missing then the Total Score is missing. Activities marked as “Not Applicable”, are not used in the computation of the Total Score. However, in order to account for “Not Applicable” activity(s), the Total Score is weighted as follows:

Total Score = Total Score x 30 / (30 minus 3 times the number of activities marked as “Not Applicable”)

CDR-SB: The CDR-Sum of the Boxes (SB) will be determined by adding the individual scores from each of the six domains. If any domain has missing data then the CDR-SB will be missing. The values in the data will need to be converted before performing the summation, as follows;

All CDR domains, except Personal Care, use (1 = 0, 2= 0.5, 3= 1, 4=2, and 5=3), for Personal Care, use (1 = 0, 2= 1, 3= 2, and 4=3).

MMSE: The MMSE is composed of 30 questions group into domains, see [Table 4](#). For each of the MMSE domains add the correct responses. If a domain has missing data then the domain is missing. From the domains compute the six items as show in Table 4. If any domain is missing then the item is missing. The MMSE Total Score (range 0 to 30) = sum of the six items. If any item score is missing then the Total Score is missing.

Table 4: MMSE Domains and Items

Domain	Score Range	Item	Score Range
1. Orientation to Time	0 to 5	1. Orientation to Time	0 to 5
2. Orientation to Place	0 to 5	2. Orientation to Place	0 to 5
3. Registration	0 to 3	3. Registration	0 to 3
4. Attention and Calculation ^a	0 to 5	4. Attention and Calculation	0 to 5
5. Recall	0 to 3	5. Recall	0 to 3
6. Naming	0 to 2	6. Language (Sum of Naming, Repetition, Comprehension, Reading, Writing, and Drawing)	0 to 9
7. Repetition	0 to 1		
8. Comprehension	0 to 3		
9. Reading	0 to 1		
10. Writing	0 to 1		
11. Drawing	0 to 1		
		Total Score	0 to 30

^a Spell WORLD Forward, then Backward score is only use if Attention and Calculation score is not available

ADAS-Cog: The ADAS-Cog is composed of 14 items, see Table 5.

Table 5: ADAS-Cog Items and Algorithm for derivation of Item Scores and Total Score

Item	Algorithm	Handling Missing Data	Score Range
1. Word Recall	Total the number of “No” responses for each trial. The subscore is the sum the scores from trials 1, 2, and 3, divide by 3.	If a trial is missing or partially done then trial score is missing. If a trial score is missing then the subscore is missing	0 to 10
2. Commands	Total the number of “No” responses from the 5 tasks	If any task is missing then the subscore is missing	0 to 5
3. Constructional Praxis	Count the number of “No” responses. The subscore is 0 = all 4 drawings correct 1 = 1 figure drawn incorrectly 2 = 2 figures drawn incorrectly 3 = 3 figures drawn incorrectly 4 = 4 figures drawn incorrectly 5 = no figures drawn, scribbles, parts of forms	If any task is missing then the subscore is missing	0 to 5
4. Delayed Word-Recall	Total the number of “No” responses.	If any response is missing then subscore is missing	0 to 10
5. Naming Objects / Fingers	Total the number of “No” responses. The subscore is 0 = 0-2 “no” responses 1 = 3-5 “no” responses 2 = 6-8 “no” responses 3 = 9-11 “no” responses 4 = 12-14 “no” responses 5 = 15-17 “no” responses	If any response is missing then subscore is missing	0 to 5
6. Ideational Praxis	Total the number of “No” responses.	If any response is missing then subscore is missing	0 to 5
7. Orientation	Total the number of “No” responses.	If any response is missing then subscore is missing	0 to 8
8. Word Recognition	For each trial, total the number of “1” responses. If the total is 12 or less, then the trial score = total. If the total is > 12 then trial score=12. The subscore is the sum the scores from trials 1, 2, and 3, divide by 3.	If a trial is missing or partially done then trial score is missing. If a trial score is missing then the subscore is missing	0 to 12
9. Remembering Test Instructions	The subscore is 0 = None, 1 = Very Mild, 2 = Mild, 3 = Moderate, 4 = Moderately Severe, 5 = Severe	If the response is missing then subscore is missing	0 to 5

10. Comprehension	The subscore is 0= None, 1= Very Mild, 2= Mild, 3= Moderate, 4= Moderately Severe, 5= Severe	If the response is missing then subscore is missing	0 to 5																					
11. Word Finding Difficulty	The subscore is 0= None, 1= Very Mild, 2= Mild, 3= Moderate, 4= Moderately Severe, 5= Severe	If the response is missing then subscore is missing	0 to 5																					
12. Spoken Language Ability	The subscore is 0= None, 1= Very Mild, 2= Mild, 3= Moderate, 4= Moderately Severe, 5= Severe	If the response is missing then subscore is missing	0 to 5																					
13. Executive Function (Maze)	The subscore is based on the total number of seconds to complete the task and/or whenever the task was stopped due to 2 errors being made, as follows; 0 = 0-30 seconds 1 = 31-60 seconds 2 = 61 – 90 seconds 3 = 91 – 120 seconds 4 = 121-239 seconds 5 = 240 seconds or at least 2 errors	If the response is missing then the subscore is missing	0 to 5																					
14. Number Cancellation	Adjusted Score = Total # correct targets crossed off minus Total # incorrect targets crossed off minus Total # times reminded of task. Then use Adjusted Score to determine the subscore as follows; 
 
 Adjusted Score	=	Subscore	
 
 ≥23	=	0	
 
 18-22	=	1	
 
 13-17	=	2	
 
 9-12	=	3	
 
 5-8	=	4	
 
 ≤4	=	5	
 
	Adjusted Score	=	Subscore	≥23	=	0	18-22	=	1	13-17	=	2	9-12	=	3	5-8	=	4	≤4	=	5	If any component of the adjusted score is missing then the subscore is missing	0 to 5
Adjusted Score	=	Subscore																						
≥23	=	0																						
18-22	=	1																						
13-17	=	2																						
9-12	=	3																						
5-8	=	4																						
≤4	=	5																						
Total Score	Total Score = sum of the subscores above	If any subscore is missing then Total Score is missing	0 to 90																					

